- Active alcohol or substance abuse in the opinion of the investigator that could impair the subject's ability to provide informed consent, participate in the study protocol or record study materials

Withdrawal of Subjects

Subjects may withdraw from the study at any time at their own request, or they may be withdrawn at any time at the discretion of the PI for safety, behavioral, or administrative reasons. If a subject does not return for a scheduled visit, every effort should be made to contact the subject, per institutional protocol. In any circumstance, every effort should be made to document subject outcome. The Investigator should inquire about the reason for withdrawal, request that the subject return for a final visit, if applicable, and follow up with the subject regarding any unresolved AE's.

Any related SAE occurring within 14 days following subject discontinuation must be reported to Osiris Therapeutics and be followed up until stabilization or resolution. If the Subject withdraws from the study, and also withdraws consent for disclosure of future information, no further study evaluations will be performed, and no additional data will be collected. The PI may retain and continue to use any data collected before such withdrawal of consent.

The Investigator may choose to withdraw their own participation or discontinue a Subject from study with

or without their consent for any of the following:

- Adverse Events
- Non-compliance
- Safety
- Complications
- Unforeseen events

A patient who experiences the noted changes, relative to previous measures, in the following parameters will be terminated early from study participation

- An increase in wound size by 50% or more prior to debridement.
- An increase in pain rating by 50% or more
- Presence of infection as determined by 2 more bacterial infection indicators that requires treatment outside the study scope
- Need for wound management outside the study scope
- Or for any reason that may, in the opinion of the Investigator, affect negatively the wellbeing of the subject.

If for any reason the subject is withdrawn from the clinical investigation, the Investigator will inform the subject accordingly.

4. Trial Design

Description of Trial Design

This study is a prospective, 2-arm parallel assignment, randomized clinical trial to compare lyopreserved vs cryopreserved Stravix as an adjunct therapy to NPWT.

Trial Endpoints

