Primary Endpoint: To compare the incidence of complete wound closure of lyopreserved vs cryopreserved Stravix treated groups at 12 weeks post initial application.

Secondary Endpoints: To evaluate the outcomes noted below between lyopreserved and cryopreserved Stravix.

1. Time to 100% granulation of deep structures (bone, tendon, etc)
2. Duration of NPWT
3. Time to surgical grafting to cover the wound.
4. Time to complete wound closure (complete epithelization with no drainage)
5. Level of infection
6. Quality of Life – SF36, EQ-5D and PROMIS®

Sample Size

For this study, 40 patients from UT Southwestern and Parkland hospitals will complete the study (no cap on screening/enrollment).

Duration of Subject Participation

- Screening: Within 7 days of therapy start
- Treatment period: Up to 12 weeks from therapy start
- Total duration of subject participation: Up to 13 weeks

Screening and Enrollment

Patients who present to the investigator's institution (through clinic admission, direct transfer from another facility, or through the emergency room) may be recruited to participate in the study. No direct marketing for subject recruitment will be done.

Patients approached for study participation will be at least 21 years of age at the time of consent, will undergo wound assessment, and meet all eligibility requirements. Those meeting eligibility criteria for the study will have the study explained to them by the Investigator. An Informed Consent Form will be provided to sign according to Section 11 prior to undergoing any study procedures. Patients will be encouraged to ask questions of the investigators. It will be made clear to the patient that not participating in the study will in no way influence the treatment plan or the relationship with the physician.

There is no cap on the number of subjects that can be screened/enrolled. Additional subjects will continue to be recruited as needed to reach the minimum number of 20 treated per protocol, per arm (40 in total).

Wound Selection

Subjects with only one wound will be included in the study. Subjects with multiple wounds will have each wound measured for volume. The wound with the largest volume meeting all eligibility requirements will be chosen for inclusion in the study as the primary wound. The etiology of the chosen wound, its classification, and if it is a new or recurring, will be documented. All other wounds will be documented as secondary wounds and will be followed throughout the study.

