11. Place Stravix (lyo or cryo per randomization schedule) and dress wound for NPWT therapy (typically within 24 hours post-operatively for NPWT placement).
12. Document size of Stravix used.
13. Disburse subject stipend

Therapy/Treatment Phase (Weekly visits +/- 4 days)

Study Visit 1-11:

1. Assess target ulcer (if wound has closed, document as such, skip to step 5).
2. Document time on/off NPWT if applicable. NPWT removal/discontinuation will be per Principal Investigator discretion.
3. Perform standardized photography (eKare) of the study primary wound when NPWT is removed.
4. Assess the ulcer(s) area (cm^2), perimeter (cm), and greatest depth (cm) using the inSight device (eKare) and document if the primary wound and, if applicable secondary wound(s), document if subject has investigational product in place or no investigational product- if the wound is deemed closed by the physician, skip to EOS visit.
5. Perform hyperspectral imaging of the dorsal and plantar aspects of the foot if wound is active or closed.
6. Debride wound if indicated. Re-measure primary wound and, if applicable, secondary wounds with the inSight device (eKare) if surgical debridement is performed prior to dressing the wound.
7. Collect tissue and/or bone samples at weeks 4, and 8. If at any visit the subject has an infection, collect tissue and/or bone.
8. Collect blood sample at week 4 (approximately 10mL at each collection) for Ribonucleic Acid

(RNA) gene expression. Will also collect blood if patient develops and recovers from an infection during the study timeframe. Blood will be collected once clinical signs of infection are resolved.

9. Collect all relevant concomitant medication.
10. If wound is still active, redress the wound with assigned Stravix (if removed for debridement) and NPWT. Document all dressings applied including size of Stravix.
11. Disburse subject stipend
12. Note: at week 4, if wound is not ready for grafting, remove existing Stravix and replace with new piece of Stravix (per randomization schedule)
13. Assess for AE/SAEs and/or follow up on previous AE/SAEs.

Study Visit Closed

1. When a subject's study wound has closed, they will perform the EOS evaluation.

Study Visit 12/EOS:

1. At the time of wound closure, subjects will perform EOS visit.
2. A subject whose wound is not deemed closed (epithelialized with no drainage) by physician at week 12 will exit from the study after the week 12 wound evaluation.
3. Assess index ulcer.

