4. If the wound is still open and large enough, collect tissue and/or bone samples along with a blood sample.
5. Assess the ulcer(s) area (cm^2), perimeter (cm), and greatest depth (cm) using the inSight device (eKare) and document if the primary wound and, if applicable, secondary wound(s) and if subject has investigational product in place or no investigational product.
6. Perform hyperspectral imaging of the dorsal and plantar aspects of the foot if wound is active or healed.
7. If wound has not closed, redress the wound per physician-directed standard of care.
8. Administer Patient Reported Outcome (PRO) (questionnaires).
9. Collect all relevant concomitant medication
10. Perform EOS visit documentation
11. Follow up on AE/SAEs that have been reported that have not yet been resolved.

Study Visit Follow-up:

1. If the wound heals during the treatment phase or if the wound is not healed after 12 weeks, data from their electronic medical record will be evaluated to identify healing, time to heal, adverse events related to the wound.

Detailed Study Operations

Medical Status/History

- *The New York Heart Association (NYHA) Functional Classification System:* This system will be used to classify stage of heart failure. The New York Heart Association (NYHA) functional classification system is used to classify the stage of heart failure from Class I to IV (as shown in the table below). This system relates symptoms to everyday activities and the patient's quality of life.

	Patient Symptoms
Class	
Class I (Mild)	No limitation of physical activity. Ordinary physical activity does not cause undue fatigue, palpitation, or dyspnea (shortness of breath).
Class II (Mild)	Slight limitation of physical activity. Comfortable at rest, but ordinary physical activity results in fatigue, palpitation, or dyspnea.
Class III (Moderate)	Marked limitation of physical activity. Comfortable at rest, but less than ordinary activity causes fatigue, palpitation, or dyspnea.
Class IV (Severe)	Unable to carry out any physical activity without discomfort. Symptoms of cardiac insufficiency at rest. If any physical activity is undertaken, discomfort is increased.

- *Body Mass Index (BMI)*: BMI is calculated as the ratio of body weight in kilograms (kgs) to height in meters squared (m^2).
- *Medical History*: The following information will be collected from each subject

Co-Morbidities

Cardiac	MI < 6mos		MI > 6mos	None		
Coronary Artery Bypass Surgery	Yes/No					

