Semmes-Weinstein monofilament evaluation will be performed. We will assess light touch and pressure sensation at five sites on the study foot using a 10-gram monofilaments. We will perform Vibration Perception Threshold VPT; a device that uses vibration to test how well your feet can detect gentle pressure.

Infection Evaluation

This system first divides wounds by whether they are clinically infected on the basis of the presence of purulent secretions or local or systemic signs of inflammation or infection. Infected wounds are further divided into those that are considered to be mild, moderate, or severe, on the basis of the size (especially of any cellulitis) and depth (or level of tissue involved) of the infection and presence of systemic manifestations of infection or metabolic instability [4]. Additionally, the subjects will have the following monitored: temperature, heart rate, respirations and WBC.

Description	International Working Group Infection Severity
no infection: no pus no inflammation	1
2 or more signs of infection (pus, pain, warmth, swelling. cellulitis < 2cm infection limited to the skin or subcutaneous tissue	2

No systemic signs of infection	
2 or more signs of infection (pus, pain, warmth, induration. cellulitis > 2 cm lymphangitis, abscess infection extends to deep fascia, tendon muscle No systemic signs of infection	3
same as 3 with systemic toxicity meets SIRS criteria fever >38C, tachycardia >90, respiration >12, leukocytosis >12,000	4
osteomyelitis	5

Patient Reported Outcomes

The Medical Outcomes Study (MOS) 36-item Short Form (SF-36) is one of the most commonly utilized instruments in assessing diabetic foot disease and provides information on overall physical and mental quality of life. The SF-36 provides a physical component summary (PCS) score as well as a mental component summary (MCS) score, which are derived from eight different sub-scales. The PCS and MCS are standardized so that a score of 50 represents the normative score for the general population, and a higher score is indicative of better HRQOL (20). Excellent correlation has been found between PCS and MCS scores calculated from the SF-36 in patients with diabetic foot disease [5].

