The EuroQol-5-dimension (EQ-5D-5L) questionnaire is a generic instrument which is commonly used for the assessment of QoL in various diseases. The 5-level version, EQ-5D-5L, consists of 2 pages – the EQ-5D-5L descriptive system, and the EQ visual analogue scale (EQ VAS). The descriptive system comprises 5 dimensions: mobility, self-care, usual activities, pain/discomfort, and anxiety/depression. Each dimension has 5 levels: no problems, slight problems, moderate problems, severe problems, and extreme problems. The digits for the 5 dimensions can be combined in a 5-digit number describing the respondent's health state. The questionnaire item results will be converted to an index score using the conversion tool provided by EuroQoL for EQ-5D-5L.

The EQ VAS records the respondent's self-rated health on a 20 cm vertical, visual analogue scale with endpoints labeled 'the best health you can imagine' and "the worst health you can imagine". This information may be used as a quantitative measure of health as judged by the individual respondents.

PROMIS® is a publicly available system of highly reliable, precise measures of patient-reported health status for physical, mental, and social well-being. This web-based resource can be used to measure health symptoms and health-related quality of life domains such as pain, fatigue, depression, and physical function, which are relevant to a variety of chronic diseases.

Offloading

All subjects who can be offloaded will wear the DH OffLoading Walker or a Total Contact Cast. Subjects who have dorsal wounds or who cannot wear a boot/cast will be placed in a diabetic shoe. Offloading method may be dependent on wound location and postural positioning of the subject.

12 Month Retrospective Follow-up:

We will collect 12 month follow-up data to extend the length of follow up to adequately capture the time period with highest incidence of recurrent ulceration and infection.

Schedule of Events Table – Treatment Phase

The table below shows the schedule of planned events for each subject in this study.

Schedule of Events															
	Weekly Visits (± 4 days)														
	SC	BL/0	1	2	3	4	5	6	7	8	9	10	11	*EOS	FUP @6mo
Informed Consent	X														
Inclusion/Exclusion	X														
Randomization	X														
Medical History, Social, Demographics, PE, Vitals		X													
Lab Values		X													
Blood Collection for RNA[#]		X				X								X	
Pregnancy test if needed	X														

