We will summarize study variables as means and standard deviations (SD) for continuous variables and proportions or percentages for categorical variables. Continuous variables will be presented as median, mean \pm standard deviation and dichotomous variables presented as percent. We will use Analysis of Variance (ANOVA) to test for differences in continuous variables. For categorical variables, we will use chi square to compare the proportion of outcomes in each treatment arm with an alpha of 0.05, and we will use Kaplan Meier analysis to compare closure rates of the treatment groups. p-values were reported using the step-up Bonferroni method of Hochberg. We will use an adjusted two-sided analysis with an alpha of 0.05. In the intent to treat analysis, we will use the last observation carried forward to define the clinical outcomes for patients that were lost to follow up.

Tissue samples will be extracted and used for molecular biology analyses. These may include, gene and protein expression of the wound tissue, histological analyses of tissue morphology and pathology, and analyses of bacterial genes to determine levels of infection. All sample analyses will be performed in a de-identified manner and tissue samples WILL NOT be used for genetic sequencing that can be used to deduce the subject's identity.

Sample Size Justification

This is a pilot exploratory study so no sample size justification will be provided.

8. Data Management

Standardized CRFs will be used. Investigators are responsible for the accurate completion and timely submission of the data collected during the trial. All data from the trial will be entered from the CRFs into a central database. Incoming data will be frequently reviewed to identify inconsistent or missing data and any adverse events. Any data issues are to be promptly addressed with the investigator by the Sponsor. Quality assurance procedures will be established to ensure that complete, accurate and timely data are submitted, that protocol requirements are followed and that complications, adverse events and adverse device effects are correctly reported and investigated, as appropriate. Investigators are to maintain all source documents as required by the protocol, including laboratory results, supporting medical records, and signed Informed Consent Forms. The source documents will be used during the regular monitoring visits to verify information from the database against data contained on the completed CRFs.

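### Infection can end study participation, and nothing clearly requires infection status to be recorded from then to week 12, although level of infection is a secondary endpoint

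*Combined protocol and SAP*

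**What the plan says.** - **Endpoint.** Sections 4 (Trial Endpoints) and 5 list level of infection as secondary endpoint 5. Infection Evaluation in section 4 gives a five-level scale headed "International Working Group Infection Severity". The Analysis Plan in section 7 also mentions "analyses of bacterial genes to determine levels of infection". The plan does not say which of the two is the endpoint, or at what time it is read.
- **Termination.** Section 3 states that a patient "will be terminated early from study participation" on any of several triggers, one of which is "Presence of infection as determined by 2 more bacterial infection indicators that requires treatment outside the study scope".
- **On-study capture.** The steps for Study Visits 1-11 say "If at any visit the subject has an infection, collect tissue and/or bone".
- **After withdrawal.** Section 3 asks for a final visit where applicable, every effort to document the outcome, and follow-up of unresolved adverse events. Section 14 asks for adverse events to be followed to resolution.
- **Chart review.** Study Visit Follow-up plans an electronic medical record (EMR) review "If the wound heals during the treatment phase or if the wound is not healed after 12 weeks". The 12 Month Retrospective Follow-up is meant "to adequately capture the time period with highest incidence of recurrent ulceration and infection".
- **Analysis and recruitment.** Intent to treat is the only analysis named, with last observation carried forward for patients lost to follow-up (section 7). Screening and Enrollment adds subjects "as needed to reach the minimum number of 20 treated per protocol, per arm (40 in total".

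**The concern.** The rule ends participation, not only treatment, and the reason is an outcome that the trial compares. A subject whose infection is bad enough to need outside treatment is the one in whom its later course matters most, and the scheduled visits stop at that point. If the infection then spreads to deep tissue, becomes systemic or reaches bone before week 12, the plan may hold no grade for it. If terminated subjects are also replaced and left out of the comparison, the infection itself drops out of the count.

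Who is terminated rests on an undefined phrase, applied by an investigator for whom the description of the trial design mentions no blinding.

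**Working it through.** The plan states no infection rate, termination rate or sample size calculation, so there is no figure to reproduce. The main check is of the text; the arithmetic at the end is illustrative.

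**1. Who is caught.** The trigger needs two or more infection indicators. On the Infection Evaluation scale, two or more signs is already grade 2, the mildest infected grade. The indicator count therefore does not separate serious from mild infection, and the undefined scope condition does the selecting. The protocol expects some infected subjects to stay: it plans blood sampling in those who become infected and recover during the study.

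**2. What the terminating visit captures.** The infection is seen on study, and the visit steps call for tissue or bone. A Schedule of Events footnote restricts tissue collection to surgical debridement, so even this sample is not certain. No visit step or schedule row sets a time for the 1-5 grade in any subject.

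**3. What could supply infection status from then to week 12.**

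| Route | What it offers | Why it does not clearly close the gap |
|---|---|---|
| Final visit (section 3) | A visit is requested | Only where applicable; content not stated |
| Adverse event follow-up (section 14) | Follows the reported event to resolution | Case report form entries run to the last subject visit; severity is rated by interference with function, not on the infection scale |
| Serious event reporting (section 14) | Runs to 28 days after the last application, later if causality is suspected | Last application at baseline: closes at day 28, 84 − 28 = 56 days before week 12. Last application at week 4: closes at day 56, 84 − 56 = 28 days before |
| EMR review (Study Visit Follow-up) | Healing, time to heal, wound-related events | Written for wounds that heal in the treatment phase or are unhealed after 12 weeks; termination is not mentioned and no grade is named |
| 12 Month Retrospective Follow-up | Aimed at recurrent ulceration and infection | Does not say which subjects are covered or that a grade is recorded |
| Last observation carried forward (section 7) | Would hold the stopping value | Written for patients lost to follow-up; terminated subjects are not said to be such |

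**4. Effect on a worst-grade summary.** Let G be the grade at the stopping visit. The true worst grade to week 12 lies between G and 5, so the understatement is at most 5 − G: three grades if G = 2, two if G = 3, one if G = 4, none if G = 5. A subject kept in the analysis is still counted as infected. Only later worsening is lost.

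**5. Illustration of a completer comparison, all rates assumed.** Let p be the true infection proportion and k the share of infected subjects terminated. Assume no other dropout, and that terminated subjects do not count towards the 20 per arm. Then the infection proportion in completers is p(1 − k)/(1 − pk), and the number randomised per arm is 20/(1 − pk), rounded up.

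| p | k | pk | Randomised per arm (total) | Completers infected | Under-count |
|---|---|---|---|---|---|
| 20% | 25% | 5% | 20/0.95 = 21.05, so 22 (44) | 0.15/0.95 = 15.8% | 4.2 points |
| 40% | 25% | 10% | 20/0.90 = 22.2, so 23 (46) | 0.30/0.90 = 33.3% | 6.7 points |
| 40% | 62.5% | 25% | 20/0.75 = 26.7, so 27 (54) | 0.15/0.75 = 20.0% | 20.0 points |

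With the same p and k in both arms the gap between arms is 0. If true rates differed, say 30% against 10%, and half of infected subjects were terminated in each arm, completers would show 0.15/0.85 = 17.6% against 0.05/0.95 = 5.3%. A 20-point difference would then appear as 12.4 points. If all randomised subjects are counted with their stopping-visit grade, the proportion infected is not under-counted in any of these cases.

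**The case against.** The other side has four good arguments.

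- **The key observation is kept.** The terminating infection occurs on study, is to be sampled, counts as a reportable wound-related event and is followed to resolution. This stands. A reader might infer that infection data are lost altogether in terminated subjects; the documents do not support that. What is at risk is the course after the stopping visit.
- **Missing grading times are a general gap.** The plan sets no time for grading in anyone, and the week 4, week 8 and end-of-study tissue samples are already conditional on surgical debridement or on a wound still open and large enough. This stands too: the termination rule did not create that gap, and scheduled samples cannot be counted as certain losses. But the rule adds something separate, because it ends the visits at which infection would be observed, and does so because of infection.
- **The chart reviews may cover these subjects.** The 12-month collection excludes no one, and a terminated subject with an open wound could fall under the 12-week condition. That is a possible reading, but neither text says so or asks for an infection grade.
- **No completer analysis is planned.** Correct. Intent to treat is the only analysis named, and the per-protocol wording is a recruitment target. The under-counts above therefore apply only if terminated subjects are left out. The plan does not say that they stay in the infection comparison.

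**Conclusion.** The point holds in a limited form. A mandatory rule stops study participation because of infection, the condition that selects subjects is undefined, and no text clearly requires infection status from the stopping visit to week 12. Later worsening can be missed selectively in these subjects, and a comparison limited to completers would under-count infection.

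No size follows from the documents. The 4.2, 6.7 and 20.0 points rest entirely on assumed rates and on an analysis the plan does not name.

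A reader might also infer that the rule biases the comparison of lyopreserved with cryopreserved product. The documents do not show this and do not exclude it. It would need terminated subjects to be left out, or their later course to be missed, unequally by arm, and nothing in the text says that either would happen.

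The change is worth making because it is cheap, but its priority is modest: one secondary endpoint in a study that calls itself a pilot.

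**What to change.** 1. Define treatment outside the study scope, for example infection that requires the study product or NPWT to be stopped.
2. Make the infection trigger a stop of study treatment, not of follow-up, with clinical care unchanged.
3. Record the Infection Evaluation grade at the stopping visit.
4. Unless consent is withdrawn, follow every randomised subject to week 12, by visit or by extending the planned EMR review expressly to terminated subjects. This fits section 3, which bars further data collection only when consent for future disclosure is also withdrawn.
5. State that level of infection is compared in all randomised subjects by the worst Infection Evaluation grade from first application through week 12, with each EMR-based grade flagged. Further subjects may be recruited, but terminated subjects stay in the analysis.

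**Cost.** A protocol amendment with IRB approval (section 11) and chart review for a few subjects at the two existing hospitals. EMR-based grades will be less complete than visit grades and will fall mainly in terminated subjects, hence the flag. Bacterial-gene results after the stop cannot be recovered from the record.

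### Duration of NPWT is recorded without a reason for stopping, so under ANOVA a failure stop counts the same as a stop because the wound was ready (minor, cheap to fix)

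*Combined protocol and SAP*

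**What the plan says.** "Duration of NPWT" appears as secondary endpoint 2 in the synopsis, in Section 4 (Trial Endpoints) and in Section 5. None of the three defines it.

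The start is clear enough. Baseline step 11 reads "Place Stravix (lyo or cryo per randomization schedule) and dress wound for NPWT therapy".

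For the end, step 2 of Study Visit 1-11 says "Document time on/off NPWT if applicable. NPWT removal/discontinuation will be per Principal Investigator discretion". Step 10 of the same list sets the default: while the wound is active, NPWT is reapplied. It adds "Document all dressings applied including size of Stravix". Neither step asks why NPWT was stopped for good.

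Section 7 (Analysis Plan) assigns no method to this endpoint by name. Three of its general rules bear on it:

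- "We will use Analysis of Variance (ANOVA) to test for differences in continuous variables"
- "we will use Kaplan Meier analysis to compare closure rates of the treatment groups", which covers closure only
- in the intent-to-treat analysis, "we will use the last observation carried forward to define the clinical outcomes for patients that were lost to follow up"

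It also says "p-values were reported using the step-up Bonferroni method of Hochberg", without stating which endpoints form the family.

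**The concern.** A short NPWT duration can mean two opposite things. The wound bed may have become ready for cover, or NPWT may have been abandoned because of infection, worsening, amputation or intolerance. A comparison of mean days cannot tell these apart.

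Failure stops are foreseeable. Section 3 ends participation for a wound that grows by half or more, for infection needing treatment beyond the study, and for wound care beyond its scope. Such subjects stay in an intent-to-treat set with a short duration. Others may come off NPWT at the investigator's discretion and remain in the study.

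What is at stake is the reading of one secondary endpoint. The arm with more failure stops could appear to need less NPWT. A reason that is not coded at the time may not be recoverable afterwards.

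**Working it through.** The plan gives no duration, standard deviation, failure rate or power figure, so there is nothing of its own to reproduce.

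**Inputs from the documents.** At least 20 subjects per arm treated per protocol, with further recruitment until that is reached (Section 4, Screening and Enrollment); 12 weeks = 84 days; two-sided alpha 0.05; six secondary endpoints in Sections 4 and 5 (the synopsis lists seven).

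**Assumptions, not from the documents.** Time to readiness is the same in both arms, gamma with mean 42 days and SD 14 or 21. Failure stops are gamma with mean 14 days and SD 7. All durations are cut at day 84, and failures are in the analysed set.

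**Step 1, by hand.** With f failures among 20 subjects, readiness at day 42 and failure at day 14:

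arm mean = [(20 - f) x 42 + f x 14] / 20

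- f = 2: (756 + 28) / 20 = 39.2 days
- f = 6: (588 + 84) / 20 = 33.6 days
- difference = 5.6 days in favour of the worse arm

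If failures are instead replaced until 20 per arm are treated per protocol, and all are analysed: (20 x 42 + 2 x 14) / 22 = 39.45 and (20 x 42 + 6 x 14) / 26 = 35.54. The difference is 3.9 days.

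**Step 2, simulation.** 20,000 trials, 20 per arm, pooled two-group t-test (the same as two-arm ANOVA). Ranges cover SD 14 and SD 21. The last two columns count only results favouring the worse arm; in the first row the arms have equal rates, so they count results favouring one given arm.

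| Failure stops | Shift in mean | Worse arm shorter | p < 0.05 | p < 0.05/6 |
|---|---|---|---|---|
| 10% v 10% | about 0 | about 50% | about 2.5% (chance) | 0.4% |
| 10% v 15% | about 1.4 days | 58-62% | about 4% | about 1% |
| 10% v 20% | 2.7-2.8 days | 66-71% | 6-8% | 1.4-1.9% |
| 10% v 30% | 5.5-5.6 days | 80-85% | 13-18% | 3.8-5.4% |

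The threshold 0.05/6 = 0.0083 is the strictest Hochberg step if the six secondary endpoints are the family. With the synopsis's seven it is 0.05/7 = 0.0071, and the last entry becomes 3.4-4.9%.

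**Step 3, week-12 cap.** In this model only 0.6% (SD 14) to 3.8% (SD 21) of the 10%-failure arm reach day 84, so the cap contributes almost nothing to the shifts above.

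**Step 4, does a readiness-based measure point the right way?** In the 10% v 30% case, the share stopped for readiness by week 12 is 86-89% in the better arm and 67-70% in the worse. It is lower in the worse arm in 90-92% of trials.

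**The case against.** Several points on the other side stand.

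- **Exposure reading.** The plan does not say that shorter is better. As a measure of therapy received, observed NPWT days are correct whatever the reason for stopping. This supports keeping total days as a description, but not testing them as though they measured progress.
- **No reason to expect imbalance.** Both arms receive Stravix and differ only in how it is preserved. Nothing in the documents suggests a threefold difference in failure stops, and with equal rates there is no bias.
- **Discretion is not the whole rule.** A reader might infer from step 2 that NPWT stops at will. Step 10 makes continuation the default while the wound is active.
- **Week 12.** A reader might see NPWT still running at week 12 as a second serious gap. Treatment lasts up to 12 weeks and the cap is the same in both arms, so days within 12 weeks is a usable measure. One clarifying line is enough.
- **Pain.** A reader might infer from Section 14 that pain leading to removal is never collected. That section leaves out only events unrelated to the product, diabetes or wound healing. Pain judged related to the product or wound is collectable, and Section 3 offers further routes to termination, after which Section 12 requires the exit reason.
- **Other records.** Weekly measurements, photographs at NPWT removal, anti-infective drugs, infection grade and wound-related adverse events allow partial reconstruction. Closure and infection level are reported alongside and could contradict a misleading mean.

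What remains is that no instruction ties these records to the removal decision. The exit reason also does not cover a subject who stops NPWT and stays in the study. The case report form is not in the documents and may already hold a reason field; even so, the analysis plan would still lack a scoring rule.

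**Conclusion.** The point holds as a minor, cheap improvement. As written, the plan lets failure stops and readiness stops count alike in a comparison of mean days, and the weekly-visit instructions ask for no reason that would separate them. The direction of the distortion is clear when failure stops differ by arm. Its size is not known: the figures above rest on assumed durations and failure rates and run from nothing (equal rates) to about 5.5 days (10% v 30%).

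A reader might go further and conclude that the endpoint is biased or that a false positive finding is likely. The documents do not support that. Bias needs unequal failure stops, for which they give no evidence. After Hochberg adjustment at its strictest step, a significant result favouring the worse arm stays at about 5% or less in the 20-per-arm illustrations. Applying ANOVA here is also an inference from the general rule for continuous variables. The endpoint is secondary, in a study that Section 7 calls a pilot, and the primary endpoint is untouched.

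**What to change.** **Definition.** Count duration from first NPWT placement at baseline to final removal, meaning off and not restarted by week 12, so that dressing changes and debridement pauses are not stops.

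**Case report form.** Beside the on/off times, record the final-removal date and one coded reason: ready for cover, grafted, closed, infection, worsening, amputation, intolerance, death, withdrawal, other. Tabulate reasons by arm.

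**Analysis.** In the intent-to-treat set, report by arm the cumulative incidence of NPWT stop for readiness, grafting or closure, with 95% confidence intervals. Count infection, worsening, amputation, intolerance and death as competing events. Censor unrelated withdrawal, loss to follow-up and NPWT still on at week 12. State in advance how stops coded as other will be assigned. Keep total NPWT days within 12 weeks as a descriptive exposure measure, not tested by ANOVA. No formal competing-risks test is needed at about 20 per arm.

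**Cost.** One removal date with its reason code, one definition sentence and one line in the analysis plan; no change to visits, procedures or sample size. The analysis is slightly more complex than a mean, partly overlaps secondary endpoints 3 and 4, and will have wide intervals. The reason code still rests on the investigator's judgement, but that judgement becomes visible.
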